## **3.4 Study Population**

### **3.4.1 Inclusion Criteria**

1. Antenatal diagnosis of CDH, with care in the Center for Fetal Treatment
  2. Gestational age  $\geq$  36 weeks at birth
-

### **3.4.2 Exclusion Criteria**

1. Multiple gestation
2. Major anomalies or aneuploidy
3. Enrolled in FETO (fetal endoluminal tracheal occlusion) trial
4. Palliative care planned or considered
5. Maternal diagnosis placenta previa, accreta, or abruption
6. Maternal diagnosis pre-eclampsia requiring Magnesium sulfate therapy at time of delivery
7. OB or Neonatal provider concerns for the clinical care of the mother or infant, or study team not available.

The inclusion and exclusion criteria are the same for the interventional arm and the historical controls. Subjects that do not meet all of the enrollment criteria may not be enrolled. Any violations of these criteria must be reported in accordance with IRB Policies and Procedures.

## **4 STUDY PROCEDURES**

### **4.1 Screening Visit**

- We will screen for potential subjects during antenatal visits in the CFDT and on an antenatal basis for women admitted to the SDU. The screening visit includes:
  - Medical Record Review
  - Informed Consent
  - The historical controls will be identified from IRB # 3799 and will be selected as the most recent historical control, matched for gestational age and CDH severity markers to allocated subjects in the interventional arm.

### **4.2 Study Treatment Phase**

#### **4.2.1 Visit 1: Delivery visit**

The delivery visit occurs when mothers of fetuses with informed consent present for delivery. The delivery visit includes:

- Medical Record Review
- Study intervention
- Video Recording of Resuscitation

#### **4.2.2 Matched Historical Controls**

Medical record review will include the specified secondary clinical outcomes for control infants.

---

### 4.3 Follow-up Phase

The follow up phase will occur for until hospital discharge and includes

- Medical Record Review

In the follow up phase, we will also ascertain the maternal experience and perspectives of participating in the DING intervention through:

- Maternal questionnaire administration
- Semi-structured maternal interview

Maternal perspectives will be ascertained through a questionnaire administered to the mother within the first month post-partum. The DING questionnaire will be provided to mothers while they are visiting their infants in the NICU. At that point, mothers can opt in to participate in a semi-structured interview to further explore their experience and views in a qualitative fashion. The interview will take place within the first month of delivery.

### 4.4 Subject Completion/Withdrawal

Subjects may withdraw from the study at any time without prejudice to their care. The Investigator may also withdraw subjects to protect the subject for reasons of safety or for administrative reasons.

It will be documented whether or not each subject completes the clinical study.

If the Investigator becomes aware of any serious, related adverse events after the subject completes or withdraws from the study, they will be recorded in the source documents and on the CRF.

#### 4.4.1 Early Termination Study Visit

All study procedures will occur during the birth hospitalization, on an inpatient basis. There is no specific early termination study visit for subjects who withdraw from the study.

## 5 STUDY EVALUATIONS AND MEASUREMENTS

### 5.1 Identification of eligible subjects

A study team member will search for patients meeting inclusion and exclusion criteria by **reviewing, but not obtaining or recording**, data from the Epic electronic health record to determine if patients are potentially eligible. Patients who are preliminarily identified as possibly eligible will be placed on a screening log that is locked in a file cabinet in a locked research office. The historical controls will come from IRB # 3799.

---

## 5.2 Screening and Monitoring Evaluations

### 5.2.1 Medical Record Review – for both interventional arm and historical controls

We will abstract the following variables from the maternal and infant chart:

- Baseline characteristics
    - Prenatal ultrasound findings
    - Gestational age at prenatal diagnosis
    - Date of birth
    - Time of birth
    - Mode of delivery
    - Gestational age
    - Birth weight
    - Sex
    - Race
    - Ethnicity
  - Type and timing of resuscitation interventions in the delivery suite and SDU:
    - Intubation
      - Number of attempts
      - Time of successful intubation
      - Tracheal intubated adverse events, using NEAR4Neos operational definitions
    - Interval between birth and UCC (for interventional arm only)
    - Chest compressions performed
    - Medications and fluids administered
    - Supplemental FiO2
    - Ventilator settings
    - Vital signs during resuscitation (temperature, heart rate, respiratory rate, blood pressure, pulse oximetry)
  - Cardiorespiratory Interventions and diagnostic tests in first 7 days of life
    - Vital signs (heart rate, pulse oximetry, blood pressure)
    - Supplemental FiO2
    - Ventilator settings
    - Vasopressors (type and dose)
    - Laboratory tests (blood gasses, complete blood count, bilirubin level)
    - Echocardiogram findings
  - Clinical outcomes during hospitalization
    - ECMO cannulation (occurrence and day of life)
    - Mortality (occurrence, day of life, and cause)
  - Maternal chart review (outcomes will be ascertained in first 7 days after delivery, or until discharge- whichever period is shorter – for interventional arm only)
    - Estimated blood loss at delivery (all deliveries)
    - Need for therapeutic uterotonics (all deliveries)
    - First post-partum hemoglobin (all deliveries)
-

- OR time (for Cesarean deliveries)
- Contamination of sterile field (for Cesarean deliveries)
- Surgical wound infection (for Cesarean deliveries)

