### **3.1.3 Follow-up Phase**

The follow-up phase will continue until hospital discharge. In this phase we will assess the infant's physiologic outcomes and the mother's perspectives of the DING intervention. Questionnaires will be administered to mothers who consent to participation in the DING trial from day 1 to 1 month post-partum. A study team member will also approach within 1 month of the infant's birth for an approximately 30 minute open-ended in-person interview.

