## **5.4 Safety Evaluation**

Subject safety will be monitored through medical record review and debriefing the clinical staff. We will monitor for the following;

- Neonatal outcomes:
    - Cord avulsion
    - Need for chest compressions during resuscitation
    - Hypothermia (first documented temperature in the SDU <36.0)
  - Maternal outcomes:
    - Any potential contamination of sterile obstetrical field
    - Surgical wound infection
    - Post-partum hemorrhage
    - Estimated blood loss
-

- Need for therapeutic uterotonics
- Any additional concerns from Obstetrical or Neonatal staff

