## **7 SAFETY MANAGEMENT**

### **7.1 Clinical Adverse Events**

Clinical adverse events (AEs) will be monitored throughout the study. Given the short duration of the study intervention, we will monitor adverse events that occur in the SDU setting and in the ensuing 24 hours (the Follow Up phase).

Because of the disease severity and protocol-driven clinical interventions for the study population, we will not classify the following events (which are typical and expected in the CDH population in the first 24 hours of life) as SAEs: mechanical ventilation, inotropic medications, or iNO.

---

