#### Risks from the study intervention:

1. Positioning the infant on the Lifestart trolley for intubation could put tension on the umbilical cord, leading to cord avulsion and bleeding. To minimize this risk, we have performed multi-disciplinary simulations in both the labor rooms and the obstetrical operating room to define the provider's roles and identify provider positions around the Lifestart trolley (**Figure 2**). In addition, the umbilical cord will be clamped immediately if the neonatologist or obstetrician has any concerns about the patient's safety or the team's ability to perform clinical interventions.
  2. There is the potential for the infant to become cold from exposure during the procedure. We will use a warmer mattress on the LifeStart trolley to minimize this risk. In addition, the intervention will last 3 minutes maximum, reducing the potential opportunity for cold stress. Once the infant is moved to the infant stabilization suite, we will monitor his/her temperature and apply ambient heat for thermoregulation.
  3. For mothers delivering via Cesarean section, there is the potential for contamination of the surgical field from the neonatal equipment. To minimize this risk, we will drape the Lifestart trolley in surgical covers and drapes, we will use sterile equipment when possible (such as suction catheters), and all
-

neonatal providers who will be in close proximity to the surgical field for the study intervention will be in sterile surgical attire.

4. Witnessing the neonatologist intubate the infant in close proximity may cause emotional distress for the parents. We will discuss their preferences before birth and offer the use of privacy screens if they do not want the intubation to be visible.

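### Surgical wound infection after Cesarean is ascertained only to day 7 or discharge, whichever comes first, so later infections are not systematically captured and the reported frequency can only be biased downward

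*Combined protocol and SAP*

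**What the plan says.** Safety is part of the primary aim (section 2.1). Section 8.4.2 gives a specific maternal hazard at Cesarean: "there is the potential for contamination of the surgical field from the neonatal equipment". Section 5.4 lists surgical wound infection among the maternal safety outcomes, sets no time window, and gives the data source: "Subject safety will be monitored through medical record review and debriefing the clinical staff".

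The window is in section 5.2.1. For the maternal chart, "outcomes will be ascertained in first 7 days after delivery, or until discharge- whichever period is shorter", in the interventional arm only. The items under that rule include "Surgical wound infection (for Cesarean deliveries").

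Other sections give different periods:
- Section 7.1: "we will monitor adverse events that occur in the SDU setting and in the ensuing 24 hours (the Follow Up phase").
- Section 3.1.3: "The follow-up phase will continue until hospital discharge".
- Section 4.4: after a subject completes or withdraws, events are recorded only if they are serious and related and the investigator happens to learn of them.

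The trial also plans maternal contact beyond the first week. Section 4.3: "Maternal perspectives will be ascertained through a questionnaire administered to the mother within the first month post-partum". Section 3.1.3, on the interview: "A study team member will also approach within 1 month of the infant's birth". The questionnaire and interview topics in section 5.5 concern the mother's experience; none asks about the wound or infection.

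**The concern.** Wound infection is the clinical outcome through which a contaminated field would harm the mother. Under section 5.2.1 an infection that appears after she goes home, or after day 7, is not looked for. A table headed simply *surgical wound infection* would then show a frequency for an unstated and probably variable period, and a reader could take it as the post-operative risk. Because the maternal review covers the interventional arm only, no comparator shares the truncation. If wound infection is among the events the DSMB reviews after every 5 subjects, its data would carry the same limit.

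**Working it through.** **Step 1. Is there a planned figure to reproduce?** No. The documents give no wound infection rate, onset timing, Cesarean share or maternal length of stay. The only count is 20 allocated dyads (sections 3.3.2 and 5.10), so there can be at most 20 Cesareans.

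**Step 2. Does another provision close the gap?**

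| Section | Period | Does it capture a wound infection after discharge or day 7? |
|---|---|---|
| 5.2.1 | Earlier of day 7 and discharge | No |
| 5.4 | None stated; chart review and staff debriefing | Not beyond 5.2.1 |
| 7.1 | SDU stay plus 24 hours | No; shorter still |
| 4.4 | After completion or withdrawal | Only passively, and only if serious and related |
| 3.1.3, 4.3, 5.5 | Maternal contact within 1 month | No item asks about it |

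An infection treated without admission might not meet the definition of a serious event in section 7.4, so section 4.4 could omit it even if the investigator heard of it. In section 5.2.1 discharge is most naturally the mother's, since the sentence concerns the maternal chart, but the text does not say so. On either reading 7 days is the maximum.

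**Step 3. Direction.** Let p be the true 1-month infection risk and c the share of infections arising inside the window. The expected recorded proportion is p × c. Since c cannot exceed 1, the recorded proportion cannot exceed p on average. No assumed rate is needed for this.

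**Step 4. Illustration of size.** All of n (Cesareans), p and c are assumptions. The chance of recording at least one infection is 1 − (1 − p × c)^n.

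Example with n = 20, p = 0.05, c = 0.25: 1 − (1 − 0.0125)^20 = 0.222. With full capture: 1 − 0.95^20 = 0.642.

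| p = 5% | c = 0.10 | c = 0.25 | c = 0.50 | c = 0.75 | c = 1.0 |
|---|---|---|---|---|---|
| n = 10 | 4.9% | 11.8% | 22.4% | 31.8% | 40.1% |
| n = 20 | 9.5% | 22.2% | 39.7% | 53.4% | 64.2% |

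For n = 20 and p from 2% to 10%, full capture gives 33.2% to 87.8%; c = 0.25 gives 9.5% to 39.7%.

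**Step 5. What a zero would mean.** With zero infections in n Cesareans the one-sided 95% upper limit is 1 − 0.05^(1/n): 13.9% for n = 20 and 25.9% for n = 10. Under the current window that limit applies to p × c, not to p, so it does not bound the 1-month risk.

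**The case against.** The strongest reply is that this is a disclosed choice in a 20-dyad pilot. The safety analysis is descriptive (section 5.9.4), there is no maternal comparator or safety threshold, and even perfect capture leaves the wide limits shown above. Contamination of the field is itself recorded (sections 5.2.1 and 5.4), staff are debriefed after each intervention, and a DSMB reviews safety events after every 5 subjects (section 8.4.1). All of that stands, and it keeps the point modest. It does not remove it: the hazard is recorded, but its clinical consequence is followed for a shorter and variable time.

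A second reply concerns the remedy. The questionnaire can be given from day 1 and is handed out while mothers visit the NICU; the interview is opt-in and may also be early. Section 4.4.1 places all study procedures within the birth hospitalization, and bereaved mothers may not be visiting. This also stands. A questionnaire item alone would not deliver ascertainment to 1 month, so the fix needs chart review and a recorded contact date as well.

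A reader might infer that most wound infections would be missed. The documents do not support that. It requires c below 0.5, and they give neither an onset distribution nor a length of stay from which c could be obtained. Nor do they support the inference that a zero count would lead the trial to declare the procedure safe for mothers; no decision rule says so.

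**Conclusion.** The point holds as a limit on one listed safety outcome. Wound infections arising after day 7 or discharge are not systematically ascertained, and the reported frequency can only err downward. The direction follows from the text alone; the size is unknown, and the figures above illustrate assumed values of n, p and c. Sections 5.2.1 and 7.1 also give different safety windows, and section 7.1 labels its 24 hours as the follow-up phase, which section 3.1.3 extends to discharge. These passages must be reconciled. The primary endpoint, sample size and historical-control comparison are unaffected. This is a worthwhile, inexpensive improvement and not a flaw that undermines the trial.

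**What to change.** 1. For surgical wound infection only, replace the section 5.2.1 window with ascertainment to 1 month post-partum. Leave the other maternal items as they are, and state whose discharge is meant.
2. Review the available maternal chart for return visits or readmission to 1 month.
3. Add one item on wound infection to the existing maternal questionnaire or interview, and record the date of that contact so that early answers are not taken as 1-month follow-up.
4. Report the number of Cesarean mothers with ascertainment to 1 month as the denominator.
5. If the present window is kept, or for any mother followed only that far, label the result *infection before discharge or day 7*.
6. Reconcile the periods in sections 5.2.1 and 7.1, and the meaning of the follow-up phase in sections 3.1.3 and 7.1.

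The cost is a wording amendment, one question and a later look at the charts of at most 20 mothers, with no new visit. The downsides are that later infections will be partly self-reported, some mothers will not be reached, and the figure may be less favourable.

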### **5.2.2 Video Recording**

Video recording is clinical standard of care for post-delivery resuscitation in the SDU. These clinically obtained videos will be reviewed as additional source documentation to confirm the sequence and timing of resuscitative interventions performed after the DING intervention.

In addition, we will mount a CHOP-owned portable video camera to the LifeStart trolley to record the DING intervention as it is performed.

### **5.2.3 Laboratory Evaluations**

No specific laboratory evaluations will be obtained specifically for this study. We will abstract data from the following laboratory tests, which are obtained as part of standard clinical care:

- Arterial blood gasses obtained in SDU and in the first 24 hours of life
- Hemoglobin from admission CBC
- Peak bilirubin level in first week of life

## **5.3 Efficacy Evaluations**

The primary outcome is successful completion of the DING intervention. After each infant is allocated to the intervention, the study team will review the resuscitation video and the medical record and will discuss the intervention with the resuscitation team. The manual of operations will be iteratively refined based on these findings. The following measures related to protocol feasibility will be documented:

- Infant successfully positioned on the table
- Successful intubation prior to cord clamping
  - If not: why not
- Number of intubation attempts
- Duration of time between birth and cord clamping

## **5.4 Safety Evaluation**

Subject safety will be monitored through medical record review and debriefing the clinical staff. We will monitor for the following;

- Neonatal outcomes:
    - Cord avulsion
    - Need for chest compressions during resuscitation
    - Hypothermia (first documented temperature in the SDU <36.0)
  - Maternal outcomes:
    - Any potential contamination of sterile obstetrical field
    - Surgical wound infection
    - Post-partum hemorrhage
    - Estimated blood loss
-

- Need for therapeutic uterotonics
- Any additional concerns from Obstetrical or Neonatal staff

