### **3.3.2 Total Number of Study Sites/Total Number of Subjects Projected**

The study will be conducted at the Children's Hospital of Philadelphia. Recruitment will stop when 20 infant-mother dyads are allocated to receive the study intervention. The total number of subjects is 40 infant-mother dyads, which includes the 20 historical controls.

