### **5.9.4 Safety Analysis**

All subjects who have been allocated to the DING intervention will be included in the safety analysis. The frequencies of AEs will be summarized. SAEs (if any) will be described in detail.

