### 5.10 Sample Size and Power

We will enroll 25 mother-infant dyads in this pilot feasibility trial in order to obtain 20 evaluable subjects. The DING intervention has not been previously studied in infants with CDH, so the objective of this trial is to determine the feasibility of this intervention. A sample size of 20, consistent with other delivery room feasibility trials, was selected to permit adequate assessment of feasibility. In addition, review and comparison of secondary outcomes will inform power analyses for a subsequent RCT of clinical outcomes. Since this is a pilot study, we do not anticipate finding statistically significant differences, though clinically significant differences may be observed. Instead, the analytic aims are to obtain estimates needed for designing future randomized trials of the DING intervention.

Approximately 40-50 infants with CDH are born in the SDU per year, ensuring the recruitment goal is feasible.

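### Cooling on the trolley is a named risk, but the only defined temperature safety measure is a yes/no at 36.0; also reporting the temperature already abstracted would be more informative at almost no cost

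*Combined protocol and SAP*

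**What the plan says.** Safety and feasibility together form the primary aim (2.1). Section 8.4.2 lists cooling among the risks of the intervention: "There is the potential for the infant to become cold from exposure during the procedure". The mitigations given there are a warmer mattress, the 3-minute limit, and temperature monitoring with ambient heat after transfer.

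Section 5.4 defines one temperature outcome, "Hypothermia (first documented temperature in the SDU <36.0", with no unit printed (Celsius is assumed here) and no reason given for the cut. The synopsis names the same event without the cut.

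The numerical value is collected. Section 5.2.1 lists "Vital signs during resuscitation (temperature, heart rate, respiratory rate, blood pressure, pulse oximetry" under a heading that reads "for both interventional arm and historical controls".

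On analysis, 5.9.1 promises ordinary descriptive summaries of the safety evaluations. Section 5.9.4 says "All subjects who have been allocated to the DING intervention will be included in the safety analysis" and "The frequencies of AEs will be summarized". Temperature is not among the secondary endpoints (5.7) that are compared with controls (5.9.3). The DSMB sees specified safety events after every 5 allocated subjects (5.11, 8.4.1); no numerical limit or expected rate for hypothermia is given.

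**The concern.** A yes/no at 36.0 treats 36.1 and 37.2 as the same result, and likewise 35.9 and 34.5. If the procedure cools infants in general by a few tenths of a degree, the effect shows in the count only to the extent that it carries infants across that one line. How many cross depends on where infants usually start.

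The DSMB is asked whether the trial adds undue risk, and 5.10 says that the analytic aim is to obtain estimates for designing later randomized trials. Both purposes are better served by the measured temperature together with the count. The plan already does this for mothers: 5.4 lists post-partum hemorrhage, an event, next to estimated blood loss, a quantity. For the named neonatal cooling risk it lists only the event.

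**Working it through.** **The plan's own figures.** There is no temperature figure to reproduce: the documents give no usual mean, SD, expected fall or hypothermia rate. The sample size is "We will enroll 25 mother-infant dyads in this pilot feasibility trial in order to obtain 20 evaluable subjects"; 20 / 0.80 = 25 would fit a 20% loss, but no loss rate is stated, and the 20 rests on precedent. The control number comes from 3.3.2: "The total number of subjects is 40 infant-mother dyads, which includes the 20 historical controls", so 20 v 20.

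**Assumptions.** First temperature is normally distributed, with usual mean 36.4 to 37.0, SD 0.4 to 0.6 and a true fall of 0.3 to 0.5 degrees. Groups are treated as independent, as the plan's tests for secondary outcomes do. Two-sided 0.05 is used for illustration.

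**Step 1: precision of the count.** For 1 of 20, the Clopper-Pearson limits are the 2.5% point of Beta(1, 20) = 0.001 and the 97.5% point of Beta(2, 19) = 0.249, so 0.1% to 25%. For 0 of 20 the interval is 0% to 17%; for 4 of 20 it is 6% to 44%.

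**Step 2: precision of the value.**
- DING mean: t(0.975, 19) × SD / √20 = 2.093 × 0.5 / 4.472 = 0.23 (0.19 at SD 0.4, 0.28 at SD 0.6).
- Difference, 20 v 20: t(0.975, 38) × SD × √(2/20) = 2.024 × 0.5 × 0.316 = 0.32 (0.26 to 0.38 over the same SDs).

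**Step 3: how many infants cross the line.** P(below 36.0) = Φ((36.0 − mean + fall) / SD). With SD 0.5 and a fall of 0.4:

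| Usual mean | Expected below 36.0 of 20, no fall | Expected of 20, with fall | P(0 or 1 event) with fall |
|---|---|---|---|
| 36.4 | 20 × Φ(−0.8) = 4.2 | 20 × Φ(0.0) = 10.0 | under 0.1% |
| 36.6 | 20 × Φ(−1.2) = 2.3 | 20 × Φ(−0.4) = 6.9 | 0.2% |
| 36.8 | 20 × Φ(−1.6) = 1.1 | 20 × Φ(−0.8) = 4.2 | 5% |
| 37.0 | 20 × Φ(−2.0) = 0.5 | 20 × Φ(−1.2) = 2.3 | 31% |

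Over 36 scenarios (means 36.4, 36.6, 36.8, 37.0; SDs 0.4, 0.5, 0.6; falls 0.3, 0.4, 0.5), 0 or 1 event is more likely than not in only 3, all at mean 37.0.

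**Step 4: information lost, for illustration only.** The plan contains no between-group safety test. If there were one, exact power over the 36 scenarios would be as follows.
- Fisher's test on the cut is below 50% in 32 of 36.
- The t test on the temperature has higher power in all 36; the smallest gain is 18.8 percentage points.
- At mean 36.6, SD 0.5, fall 0.4: 29.5% on the cut, 69% on the temperature. At mean 37.0 with the same SD and fall: 5% and 69%.
- The t test is itself below 80% in 24 of 36. For a fall of 0.3 it has 64%, 46% and 34% power at SD 0.4, 0.5 and 0.6.

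**The case against.** **A threshold count is a legitimate safety measure.** It is closer to clinical meaning than a mean shift and suits a DSMB looking for undue risk. This stands, and is why the count should stay.

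**A reader might infer that general cooling is likely to go unseen, with 0 or 1 events taken as reassurance.** The documents do not support that. They give no baseline, and they do not say how a low count would be read. In most of the assumed scenarios several infants would fall below 36.0; a low count is the likely result only at the warm end.

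**A reader might infer that the plan limits safety reporting to frequencies.** It does not. The sentence in 5.9.4 concerns AEs, while 5.9.1 promises descriptive summaries of the safety evaluations, and estimated blood loss is already a quantity. A temperature mean is not barred; it is simply not named.

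**A reader might infer that the recorded temperatures would settle the question.** They would not. The half-width for a 20 v 20 difference at SD 0.5, 0.32, exceeds a fall of 0.3. Without a comparator, even a well-estimated DING mean cannot show a fall.

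**Individual cold infants may be noticed anyway.** The investigator reviews the record and video and debriefs staff after each procedure (8.4.1), and temperature is monitored after transfer (8.4.2). This stands for single cases, but commits no one to a group summary or to showing values to the DSMB.

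**Control temperatures may not be available.** The heading of 5.2.1 covers both groups, but 4.2.2 and 5.9.3 describe control ascertainment in terms of the secondary outcomes, which exclude temperature. The control part of the fix must therefore be conditional.

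**Conclusion.** The point holds as a cheap improvement. The sole defined temperature safety measure is a yes/no at 36.0, although the value is already abstracted and would say more about a risk that the protocol itself names. The precision figures (0.1% to 25% for 1 of 20, against about ±0.23 degrees for the mean and ±0.32 for a difference) rest on an assumed SD of 0.5 for the temperature part and on no assumption beyond the binomial for the count. How much the cut hides ranges from little, if infants usually arrive near 36.4, to a great deal, if they arrive near 37.0; the documents do not say which applies. The power figures illustrate lost information and do not show a failed calculation: 5.10 states that significant differences are not expected. No figure in the plan is wrong.

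**What to change.** In 5.4 and 5.9.4:

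- Keep the count below 36.0.
- Add the first SDU temperature as a continuous safety measure, reported as mean or median, lowest value and 95% CI.
- List the individual first temperatures for the DSMB at each 5-subject review.
- Where the same field is available for the matched controls, give the mean difference with its 95% CI, labelled as descriptive estimation and not as a test.

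The cost is a few words of plan text, one extra table row and a short listing for the DSMB. The DING infants need no new measurement; for controls, availability of the field should be confirmed first. The one drawback, that a mean shift is less directly clinical than a count, is met by reporting both.
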